## Participant Withdrawal

Participants may withdraw from the study at any time. The PI may choose to withdraw participants from the study if the participant's status changes (e.g., health change, becomes incarcerated), is suspected of intentionally providing false data, or other reasons that would lead to poor data quality (e.g., very poor performance in impulsivity tasks). Data from withdrawn participants will be evaluated on a case by case basis. For participants that withdraw themselves from the study, we will use data they provided prior to withdrawing. If the PI chooses to withdraw the participant, data will only be used if it meets quality control standards (e.g., adequate behavioral performance, limited missing data).

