### IV. Informed Consent Process

Upon initial contact, the study will be briefly introduced to the participant by a member of the research team. Participants will then complete a preliminary screen over the phone. Identifiable information will be retained for those participants who do not meet inclusion criteria only for the duration of the study to ensure that the same participant does not attempt to enroll a second time. If the participant meets inclusion criteria, the study visit will be scheduled and a copy of the consent document will be sent to them in advance if requested. Participants requesting the consent ahead of their visit will be allowed as much time as they need to decide whether or not to participate, and the PI or study staff will be available to answer questions about the consent/study procedures while the participant is making their decision. When the participant arrives for their appointment, they will be seated in a private room and given time to read the consent form with a study team member present. After the participant has finished reading the consent form, the study is described more fully by the research team and the participant is asked whether they have any questions regarding the described procedures and risks/benefits. Participants must elect to participate and can choose to discontinue their participation in the study at any time. No coercion or undue influence will be used. Additionally, participants can be withdrawn from the study by the PIs for any reason (e.g., not paying attention to tasks, failure to attend scheduled appointments, not following directions, safety concerns) throughout the course of the study

If there are no further questions, the consent form is signed and stored in a locked cabinet in a locked office at MRN. A copy of the consent will be given to the participant.

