## II. Data Analysis/Statistical Considerations

Primary and secondary outcomes will be evaluated using mixed linear effects models with condition (lorcaserin, placebo) as a within-subjects factor and medication order as a between-subjects factor. Maximum likelihood estimation will be used to account for missing data by analyzing all available cases. The primary outcomes are 1) minutes of resistance to smoking reinstatement and 2) number of half cigarettes smoked during the ad lib session. Using the same model, we will also examine secondary outcomes including: impulsive choice (k value from monetary discounting task and cigarette discounting task), impulsive action (commission errors on CPT), and reward response bias as measured by the Reward Responsiveness Test.

Statistical Power. To achieve adequate power (.80) to detect medium effects of medication on our primary outcomes, we will recruit a sample of 42 smokers in order to arrive at a final sample of 34 (allowing for up to 20% attrition). Given no prior data on lorcaserin's effects on laboratory outcomes, we reviewed effects reported in similar screening studies with other medications. In a study using the lapse paradigm proposed here, varenicline had a medium to-large effect on duration to reinstatement (Cohen's d = .72) and a large effect for self-administration (d = 1.5). To account for the possibility of stronger effects for varenicline relative to lorcaserin, our power analyses assumed a medium effect size. We assumed a within-subjects correlation of 0.60 for laboratory outcomes (as reported in prior human laboratory screening studies) and an alpha level of .05. We estimated power in G\*Power software using a fixed effects, within-subjects design and two time-points. Conservatively, a sample of N = 34 allows sufficient power (.80) to detect a medium effect on the primary outcomes (Specific Aims 1 and 2). Although human data are not available to inform the predicted effect size for Aim 2, preclinical studies using this medication, and an analogous behavioral task, suggest large effects of medication. For our supplementary aim (evaluating indirect effects on the primary outcomes via impulsivity and craving), simulation studies indicate that the proposed analysis, utilizing a bootstrap procedure, will provide sufficient power (.80), given the planned sample size, to detect mediated effects in medium-to-large effect size range.

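### The limited-missing-data condition on investigator-withdrawn participants works against the all-available-cases analysis and makes use of a valid session 1 depend on who ended participation

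*Combined protocol and SAP*

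**What the plan says.** Three rules in Participant Withdrawal bear on this point.

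- All withdrawals: "Data from withdrawn participants will be evaluated on a case by case basis".
- Self-withdrawal: "For participants that withdraw themselves from the study, we will use data they provided prior to withdrawing". No quality or completeness condition is attached.
- Withdrawal by the investigator: "data will only be used if it meets quality control standards (e.g., adequate behavioral performance, limited missing data"). No threshold is given for either example, and nothing says the decision comes before unblinding.

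The investigator's grounds are wide. Participant Withdrawal lists a change of status (for example in health), suspected false data, and "other reasons that would lead to poor data quality (e.g., very poor performance in impulsivity tasks"). Section IV, Informed Consent Process, allows withdrawal for any reason, with the examples "not paying attention to tasks, failure to attend scheduled appointments, not following directions, safety concerns".

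The analysis section (Project Data, II. Data Analysis/Statistical Considerations) says: "Maximum likelihood estimation will be used to account for missing data by analyzing all available cases". It states no exception, defines no analysis population, and plans no sensitivity analysis that would connect this sentence to the withdrawal rules.

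**The concern.** Both primary outcomes, minutes of resistance and cigarettes smoked ad libitum, are measured only at the two laboratory sessions. Someone withdrawn between the sessions has one of two primary observations. A likelihood-based mixed model is chosen so that such a person still contributes. If dropout depends on what was seen at session 1, keeping session 1 in the model is what protects the treatment estimate. A criterion that can remove a record because other data are missing takes away that protection.

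The criterion also does not track data quality. Two participants with the same side effect and an equally sound session 1 can be handled differently only because one left and the other was withdrawn. Missed appointments can cause the withdrawal that then brings the missingness criterion into play.

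At stake are a possible selection bias in the primary comparison and an analysed sample that depends on an unspecified judgement not tied to the blinded period. With 42 recruited and 34 expected to finish, a few records are a visible share.

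**Working it through.** **1. The plan's own figure.** Power of .80 at N = 34, with 42 recruited. The plan gives no number for a medium effect, so I take a standardised paired difference dz = 0.5, two-sided alpha .05. The noncentrality is 0.5 × √34 = 2.92 on 33 degrees of freedom, which gives power 0.808, so the figure reproduces. With d = 0.5 and the stated correlation of 0.60, dz = 0.5/√(2 × 0.4) = 0.559, power is 0.886 and N = 28 suffices. That fits the plan's description of its calculation as conservative. Attrition: 42 × 0.8 = 33.6, so about 8 losses are allowed for. Nothing here needs to change.

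**2. The rules side by side, for a participant with a valid session 1 and no session 2.**

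| Who ended participation | Withdrawal section | Statistical section |
|---|---|---|
| Participant | Session 1 used | Session 1 used |
| Investigator, for health change, missed visit or safety | Session 1 used only if quality standards are met, limited missingness being one example | Session 1 used |

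The sections can diverge only in the second row, and only through the missingness example.

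**3. Precision.** Assume SD 1, correlation 0.60, and treatment and period terms. With 34 completers, SE = √(2 × (1 − 0.6)/34) = √0.02353 = 0.1534. Adding 8 participants with session 1 only lowers it to 0.1499 (0.1504 with an order term as well). The ratio 0.1499/0.1534 = 0.977 is a gain of about 2%. Discarding these records therefore costs little precision, and any harm is selection.

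**4. Bias.** Crossover trials were simulated with assumed inputs: N = 42, 1:1 order, true effect 0.50 SD, correlation 0.60, and condition and session in the model. Estimation was by generalised least squares, β = (Σ XᵢᵀV⁻¹Xᵢ)⁻¹ Σ XᵢᵀV⁻¹yᵢ, with V known. Withdrawn participants contribute either their session-1 row or nothing. Relative bias is (mean estimate − 0.50)/0.50.

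| Who is withdrawn after session 1 | Session 1 kept | Session 1 dropped | Bias when dropped |
|---|---|---|---|
| 4, strictly lowest on session-1 resistance | 0.501 | 0.475 | −5% |
| 8, strictly lowest | 0.495 | 0.457 | −9% |
| 8, withdrawal tendency correlated 0.6 with session 1 | about 0.50 | 0.485 | −3% |
| 8, correlated 0.3 | about 0.50 | 0.497 | −0.6% |
| Unrelated to session 1 | 0.50 | 0.50 | none |

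The strict-ranking rows rest on 4,000 trials each. With a trial-to-trial SD near 0.15, Monte Carlo error is about 0.15/√4000 = 0.002. Repeat runs of the dropped estimate gave 0.471 to 0.477 for 4 withdrawn and 0.457 to 0.463 for 8. With no true effect there was no bias, and the rejection rate was 4.8%.

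**The case against.** The strongest reply is that the two sections do not flatly conflict. The missingness condition is only an example of a quality standard, applied by judgement. It might refer to unfinished tasks within an attended session rather than to an absent second session. All available cases might also mean all cases that pass quality control. This stands in part. A reader might infer that everyone lacking session 2 is dropped and that the plan amounts to a completer analysis for these participants. The documents do not say so: exclusion is possible under the wording, not certain. Equally, nothing in the wording protects such a record.

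Second, stricter screening of investigator-withdrawn data has a rationale, because two of the three grounds in Participant Withdrawal concern false or poor data. This stands, and the behavioural-performance screen and the exclusion of suspected false data should remain. It does not justify the missingness criterion for someone withdrawn for health, safety or a missed visit.

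Third, a reader might take 0 to 9% as the plausible range of bias. The documents do not support that. The 20% is total attrition, including self-withdrawers, whose data are kept, and some losses may precede session 1. No section makes low resistance a withdrawal ground. Participants who change their quit intentions are excused (Plan for Preventing/Minimizing Risks), and they might instead be high resisters. In the symmetric model used here, ranking from the top would shrink the estimate equally, but the plan establishes neither pattern. It also does not say which data rule covers those participants. Finally, double blinding limits deliberate selection by arm, although not selection on outcome.

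**Conclusion.** The point holds as a mismatch of wording with a modest possible effect. The plan allows sound pre-withdrawal data to be excluded for missingness when the investigator ends participation and never when the participant does. That works against its own likelihood analysis.

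Under the assumed inputs, the treatment effect is not understated when withdrawal is unrelated to session 1, and is understated by about 1–3% with moderate dependence. The 5–9% figure is a worst case. It needs all 4 to 8 losses to be investigator-initiated, to fall after session 1, to be strictly the lowest scorers, and to be discarded every time. The results also assume a normal outcome, whereas minutes of resistance are capped at 50. The number of investigator withdrawals cannot be known from the documents.

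Precision changes by about 2%, and the stated power and sample size are unaffected. The change is worth making because it is cheap and settles beforehand which records count, not because a large bias has been shown.

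**What to change.** In Participant Withdrawal:

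1. Delete the limited-missing-data example from the last sentence. Keep the behavioural-performance screen.
2. Add: outcome data validly collected before withdrawal enter the mixed models whoever initiated the withdrawal, and the absence of a later session is not a quality failure.
3. Replace the sentence that leaves withdrawn participants' data to individual judgement with: quality exclusions (for example suspected false data, unusable task data or a failed procedure) are applied to the affected measure, and are decided and recorded before unblinding.

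This aligns the section with the statistical section and still allows credibly suspected false data to be excluded. It costs a few sentences and needs no new data, participants or procedures. The only downside is that a few single-session records enter the model, which the planned estimation method already accommodates.

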### PRIOR APPROVALS/REVIEWED AT OTHER IRBS

MRN Departmental Review

## **ATTACHMENTS**

Advertisements:

Cig Flyer M1

Cig Flyer M2

## Measures (listed alphabetical):

Alcohol Purchase Task

**AUDIT** 

Cigarette Evaluation Scale

CES-D

Contemplation Ladder

Cigarette Purchase Task

Daily Survey

Demographics form

Fagerstrom Test for Nicotine Dependence

Locator form

Monetary Choice Questionnaire

Minnesota Nicotine Withdrawal Scale

Nicotine Dependence Syndrome Scale

Positive and Negative Affect Scale

Reward Based Eating Drive Scale

Self Rating of the Effects of Alcohol Questionnaire

Simplified Nutritional Appetite Questionnaire

Three Factor Eating Questionnaire

Tiffany Questionnaire of Smoking Urges

**UPPS-P Impulsivity Questionnaire** 

### **Data Collection Forms:**

Study Med Count Vitals Conconcomittent Meds Medical History Physcial Exam SAFTEE

#### Other

SAE Report

SAE Report follow-up

Adherece Handout

Belvig prescribing information

Lexicomp report for lorcaserin

MRN Departmental Review Form

Grant application

Data safety monitoring plan
